6.4. Follow-Up

6.4.1. Safety Follow-Up

The safety follow-up period is the interval between the EOT visit and the scheduled follow-up visit, which should occur 30 to 35 days after the EOT visit (or after the last dose of study treatment if the EOT visit was not performed). Adverse events and SAEs must be reported up until at least 30 days after the last dose of study treatment, the date of the follow-up visit, or until toxicities resolve, return to baseline, or are deemed irreversible, whichever is longer. Reasonable efforts should be made to have the subject return for the follow-up visit and report any AEs that may occur during this period.

If a subject is scheduled to begin a new anticancer therapy before the end of the safety follow-up period, then the safety follow-up visit should be performed before new anticancer therapy is started. Once new anticancer therapy has been initiated, the subject will move into the survival follow-up period.

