The occurrence of AEs should be sought by nondirective questioning of the subject during the screening process after signing the ICF and at each visit during the study. Adverse events may also be detected when they are volunteered by the subject during the screening process or between visits, or through physical examination, laboratory test, or other assessments. To the extent possible, each AE should be evaluated to determine:

- The severity grade (CTCAE Grade 1 to 5).
- Whether there is at least a reasonable possibility that the AE is related to the study treatment: suspected (yes) or not suspected (no).
- The start and end dates, unless unresolved at final follow-up.
- The action taken with regard to study drug.
- The event outcome (e.g., not recovered/not resolved, recovered/resolved, recovering/resolving, recovered/resolved with sequelae, fatal, unknown).
- The seriousness, as per serious adverse event (SAE) definition provided in Section 8.3.1.

Unlike routine safety assessments, SAEs are monitored continuously and have special reporting requirements (see Section 8.3.2).

All AEs should be treated appropriately. If an AE is treated with a concomitant medication or non-drug therapy, this action should be recorded on Adverse Event form and the treatment should be specified on the Prior/Concomitant Medications or Procedures and Non-Drug Therapy form in the eCRF.

Once an AE is detected, it should be followed until it has resolved or until it is judged to be permanent; assessment should be made at each visit (or more frequently if necessary) of any changes in severity, the suspected relationship to the study drug, the interventions required to treat the event, and the outcome.

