### 9.2.2. Adverse Events of Special Interest

The number of participants who experienced any TEAEs of special interest listed below will be tabulated by maximum severity.

- Colitis
- Diarrhea
- Exfoliative dermatitis
- Febrile neutropenia
- Intestinal perforation
- Rash
- Pneumonitis
- Pneumonia
- PJP infection
- CMV infection
- Herpes simplex
- Varicella zoster virus infection

The time to onset of a TEAE is defined as the interval between the date of first dose of study drug and the date of the first occurrence of a TEAE. Participants who have not experienced a TEAE at the time of analysis will be right-censored at the earlier of 30 days after the last dose date and date of last study visit through the end of safety follow-up. If participants have missing or partial last dose dates of study drug or onset date of a TEAE, the partial or missing dates will be handled using the rules explained in Section 4.1.4.

Summaries of time to onset of new or worsening Grade 3 or higher AEs will be provided using descriptive statistics and the life-table method for rash, colitis, diarrhea, febrile neutropenia, pneumonia, herpes simplex, and varicella zoster virus infection. In addition, summaries of time to onset of new or worsening AEs of any grade will be provided using descriptive statistics and the life-table method for colitis, diarrhea, exfoliative dermatitis, intestinal perforation, pneumonia, pneumonitis, PJP infection, CMV infection, herpes simplex, and varicella zoster virus infection. Kaplan-Meier plots of time to onset of new or worsening Grade 3 or higher AEs will be provided for rash, colitis, and diarrhea. In addition, Kaplan-Meier plots of time to onset of new or worsening AEs of any grade will be provided for colitis and diarrhea.

Descriptive statistics of time to onset of these TEAEs of special interest are based on all participants who have experienced a TEAE at the time of analysis. To summarize these TEAEs of special interest using the life-table method, the effective sample size is defined as the number of participants at the beginning of interval minus half the participants censored in the interval. The conditional proportion is calculated as the number of first events divided by the effective sample size in the interval.

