The longest duration of a TEAE of any grade is defined as the longest interval between the date of occurrence of a TEAE and the date of resolution. The longest duration of a Grade 3 or higher TEAE is defined as the longest interval between the date of occurrence of a Grade 3 or higher TEAE and the date of improvement to Grade 2 or lower. If participants have missing or partial onset/end date of a TEAE, the partial or missing dates will be handled using the rules explained in Section 4.1.4. Participants who have missing end date of a TEAE at the time of analysis will be right-censored using the following algorithm:

- If the TEAE is serious, then the participant will be censored at the earlier date of data cutoff, study discontinuation, and death.
- If the TEAE is not serious,
  - If the participant is ongoing with study treatment, then the participant will be censored at the data cutoff date, OR
  - If the participant discontinued treatment, then the participant will be censored at date of safety follow-up visit, or 35 days after the end of treatment visit (or after the last dose if the end of treatment visit was not performed), whichever is later; the censored date will be truncated by the earlier date of data cutoff, study discontinuation, and death if beyond.

Longest duration of new or worsening Grade 3 or higher colitis, diarrhea, rash, and febrile neutropenia will be summarized. In addition, longest duration of new or worsening AEs of any grade will be summarized for colitis, diarrhea, and rash.

The total number of participants whose TEAE of any grade resolved or whose Grade 3 or higher TEAE improved to Grade 2 or lower and the number of participants censored will be summarized. The Kaplan-Meier estimate of median time to resolution/improvement and its 95% CIs will be provided, with the CIs calculated using the generalization of Brookmeyer and Crowley's method (1982) with log-log transformation (Klein and Moeschberger 1997). Resolution/improvement rates at selected timepoints will also be provided with 95% CIs calculated using Greenwood's formula to estimate the standard error.

TEAEs of special interest to be summarized may be adjusted based on emerging data.

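### The censoring date for unresolved non-serious AEs after treatment stops can fall up to about 35 days past the last AE observation, so AE duration may be overstated

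*SAP*

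**What the plan says.** SAP 9.2.2 (Adverse Events of Special Interest) defines the longest duration of selected TEAEs and analyses time to resolution, or to improvement to Grade 2 or lower, by Kaplan-Meier. For a non-serious event with a missing end date in a participant who has stopped treatment, it says: "then the participant will be censored at date of safety follow-up visit, or 35 days after the end of treatment visit". The alternative anchor and the choice between dates follow: "or after the last dose if the end of treatment visit was not performed), whichever is later". The sentence ends with a limit: "the censored date will be truncated by the earlier date of data cutoff, study discontinuation, and death if beyond".

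The same section censors time to onset differently: participants without the event are "right-censored at the earlier of 30 days after the last dose date and date of last study visit".

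Protocol 6.4.1 (Safety Follow-Up) plans the visit, "which should occur 30 to 35 days after the EOT visit". It does not guarantee it: "Reasonable efforts should be made to have the subject return for the follow-up visit". It also allows an early visit: if new anticancer therapy is due, "then the safety follow-up visit should be performed before new anticancer therapy is started", and the subject then moves to survival follow-up. Protocol 8.1.2 (Reporting) asks for more than a single visit: "Once an AE is detected, it should be followed until it has resolved or until it is judged to be permanent".

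**The concern.** A right-censoring time should be the last time at which the event was known to be ongoing. Here it is a calendar allowance. Because the rule takes the later date, a participant last asked about AEs at the end-of-treatment (EOT) visit can be carried as unresolved to EOT + 35 days. During those days the participant counts in the Kaplan-Meier risk set, but a resolution that nobody records cannot count as an event. The denominator is kept and the numerator is lost, so the estimated duration moves up and the resolution rates move down.

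The events exposed to this are those still open when treatment stops. The outputs exposed are the duration summaries for Grade 3 or higher colitis, diarrhea, rash and febrile neutropenia, and for colitis, diarrhea and rash of any grade. SAP 11.2 says the duration summaries were added to understand how long class-effect AEs, and AEs influenced by the regimens, last.

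**Working it through.** The documents give no figure for this rule, so there is nothing to reproduce. The check has three parts.

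**1. Days credited beyond the last observation.** Take the EOT visit as day 0. Let V be the day of the safety visit (if done) and L the last day on which AE status was assessed.

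Censoring day C = min{ max(V, 35), data cutoff, study discontinuation, death }; unobserved days = C − L.

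| Situation (cutoff and death later) | C | L | C − L |
|---|---|---|---|
| Safety visit day 40 | 40 | 40 | 0 |
| Safety visit day 35 | 35 | 35 | 0 |
| Safety visit day 30 | 35 | 30 | 5 |
| Early visit day 7, before new therapy | 35 | 7 | 28 |
| No visit, still in study | 35 | 0 | 35 |
| No visit, left study on day 10 | 10 | 0 | 10 |
| No visit, left study on day 0 | 0 | 0 | 0 |

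Example: Grade 3 diarrhea starts 10 days before EOT, there is no safety visit and no other AE contact, and the participant stays in the study. Observed unresolved time is 10 days; the censoring time is 10 + 35 = 45 days. If the EOT visit was missed, the anchor is the last dose, which can fall after the last visit, so 35 is approximate and not a strict maximum.

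**2. Can the gap arise under the protocol?** The truncation acts at cutoff, at death or when the participant leaves the study. Protocol 5.7 lists death, loss to follow-up, consent withdrawal and study termination as reasons for leaving; a missed or early safety visit alone is not among them. Protocol Table 6 schedules AE assessment at EOT and at the safety visit, but not in disease or survival follow-up. The survival contacts in Protocol 6.4.3, every 12 weeks, collect later treatment, tumor assessments and survival. So the gap can occur.

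The SAP's other rules stop at the last observation: the last visit with a nonmissing grade for laboratory events (9.3.4) and the last valid radiologic assessment for participants without progression (Table 2). The time-to-onset rule takes the earlier date.

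**3. Size, by simulation.** None of these inputs comes from the documents: exponential durations in whole days with true median 7, 14, 28 or 56; 20% or 50% of events starting in the last 28 days before EOT, the rest earlier; 10%, 30% or 50% of participants still in the study with no AE contact after EOT, the rest seen on days 30 to 35; resolutions after the last contact never recorded; 200,000 events per scenario. Each cell gives the SAP rule / censoring at last contact.

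| True median (days) | Median: 20% late, 10% no contact | Median: 50% late, 50% no contact | Unresolved at day 28: 20%, 10% | Unresolved at day 28: 50%, 50% |
|---|---|---|---|---|
| 7 | 7 / 7 | 8 / 8 | 0.067 / 0.061 | 0.133 / 0.062 |
| 14 | 15 / 15 | 16 / 14 | 0.256 / 0.250 | 0.323 / 0.249 |
| 28 | 29 / 28 | 35 / 28 | 0.503 / 0.498 | 0.555 / 0.499 |
| 56 | 58 / 56 | 70 / 56 | 0.710 / 0.707 | 0.741 / 0.707 |

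Across all scenarios the median under the SAP rule exceeded that under last-contact censoring by 0 to 70 − 56 = 14 days. Last-contact censoring came within one day of the simulated true median throughout.

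With everyone seen on days 30 to 35 and all events starting in the last 28 days, the two rules gave the same median at true values of 14 (14 and 14) and 28 (29 and 29). At 56 days, close to the longest possible follow-up of 28 + 35 = 63 days, the SAP rule left the median not reached, against 57.

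**The case against.** A reader might infer that everyone without a safety visit is given 35 extra days and that AE duration therefore is overstated. The documents do not support that, for four reasons.

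- The truncation removes the days after death, withdrawal, recorded loss to follow-up or data cutoff. Several of these are natural reasons for missing the visit.
- The protocol asks for AE follow-up beyond the visit: at least 30 days after EOT, or longer until drug-related toxicity resolves (5.5.2), and until resolution or permanence (8.1.2). Where that yields an end date, the censoring rule is not used. Where status was in fact followed to day 35, the days are not unobserved.
- The 45 days in the example is a censored time, meaning longer than 45, and not a recorded duration. If the event truly was ongoing, there is no bias.
- For visits on schedule the excess is at most 5 days.

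The comparison with time to onset is also only partly like for like. Its 30-day limit follows from the TEAE definition, and resolution has no such limit; only the part that stops at the last study visit bears on this point.

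All of this stands, and it limits the point to participants who remain in the study with an early or missed visit and no other AE contact. It does not make the rule right for them. The rule can also err the other way: an event documented as ongoing after both the safety visit and EOT + 35 days loses observed follow-up.

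**Conclusion.** The point holds as a possible bias in a descriptive safety summary. For a participant still in the study with a missed or early safety visit and no other AE contact, censoring can fall up to about 35 days after the last observation. Resolutions missed in that gap push Kaplan-Meier durations up and resolution rates down.

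Whether the reported durations will be overstated, and by how much, depends on how many participants lack contact, which the documents do not give. The simulated shift of 0 to 14 days rests wholly on assumed contact rates and exponential durations; its upper end needs half of the participants to have no contact, half of the events to start late and a true median of 56 days. If most participants are seen on schedule, the effect is small unless the true median lies near the end of follow-up. Any bias runs against the drug, towards longer toxicity. The primary endpoint and AE incidence are untouched. This is an inexpensive improvement and not a serious flaw.

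**What to change.** In SAP 9.2.2, replace the later-of-two-dates rule for non-serious events after treatment discontinuation. Censor at the last date on which AE status was assessed with the event still ongoing: the safety follow-up visit if done, or a later documented AE contact; otherwise the EOT visit or the last documented AE contact. Keep the existing truncation at data cutoff, study discontinuation and death. At minimum, keep the present rule and run this one as a sensitivity analysis.

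The cost is one SAP sentence and minor programming on visit dates already collected, with no new visits. Some events will have slightly shorter follow-up. The documents do not show that the eCRF records, visit by visit, whether each event is still ongoing; if it does not, use the date of the last visit with an AE assessment.

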INCB050465 is being evaluated as a monotherapy in a Phase 1/2, dose-escalation and expansion study (INCB 50465-101, NCT02018861; Phillips et al 2016). As of 18 AUG 2017, data were available for 72 subjects who received INCB050465 administered orally at QD doses of 5 mg (n = 1), 10 mg (n = 3), 15 mg (n = 3), 20 mg (n = 34), 30 mg (n = 27), and 45 mg (n = 4). The median duration of treatment was 122.5 days (range: 7-690). Adverse events observed in \geq 20% of subjects were nausea (36%), diarrhea (35%), fatigue and rash (each 31%), and cough and vomiting (each 24%). New or worsening \geq Grade 3 anemia, thrombocytopenia, and neutropenia occurred in 7%, 10%, and 20% of subjects, respectively. No \geq Grade 3 nonhematological treatment-related AEs were reported in \geq 10% of subjects. Serious AEs that occurred in \geq 2 subjects included diarrhea (n = 5); pyrexia (n = 4); colitis, sepsis, and hypotension (n = 3 each); and ventricular tachycardia, pneumonia, exfoliative dermatitis, respiratory failure, syncope, urinary tract infection, bronchitis, and bacteremia (n = 2 each). Fourteen (19%) of the 72 subjects discontinued study treatment due to the following 10 AEs: diarrhea (n = 3); exfoliative dermatitis and colitis (n = 2 each); and pneumonitis, rash, psoriasis, neutropenia, pleural effusion, cytomegalovirus colitis, and hypercalcemia (n = 1 each). No liver function test abnormalities > Grade 1 were reported while subjects were receiving study treatment. No dose-limiting toxicities were identified, and the maximum tolerated dose was not reached.

Pharmacokinetics analysis showed the t_{max} is 0.5 to 1 hour, the terminal half-life is approximately 8 to 12 hours, and exposure appeared to be dose-proportional between 5 mg QD and 45 mg QD at steady state. The pharmacodynamic analyses demonstrated robust and sustained pathway inhibition at all dose levels tested (Phillips et al 2016). Refer to the IB for further details (IB).

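### SAP 9.2.2 counts late resolutions of non-serious off-treatment TEAEs but censors open ones near EOT + 35 days, so late Kaplan-Meier resolution rates can be slightly too high

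*SAP*

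**What the plan says.** SAP 9.2.2 (Adverse Events of Special Interest) plans the longest duration of any-grade colitis, diarrhea and rash, and of Grade 3 or higher colitis, diarrhea, rash and febrile neutropenia. The output is a Kaplan-Meier median and resolution or improvement rates at timepoints not yet named (Appendix A, Table 3.2.29 and Figure 4.5.2).

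- **Resolved events.** Duration runs to the recorded date of resolution (any grade) or of improvement to Grade 2 or lower (Grade 3 or higher). No upper limit is set.
- **Open events.** "Participants who have missing end date of a TEAE at the time of analysis will be right-censored using the following algorithm". The rule has three branches:
  - Serious: "If the TEAE is serious, then the participant will be censored at the earlier date of data cutoff, study discontinuation, and death".
  - Non-serious, on treatment: data cutoff.
  - Non-serious, off treatment: "the participant will be censored at date of safety follow-up visit, or 35 days after the end of treatment visit". The later of these two dates applies, and the 35 days are counted from last dose where that visit did not take place. Cutoff, study discontinuation or death can only move this date earlier.

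SAP 4.1.4 completes partial end dates and leaves a fully missing one alone. It sets no limit tied to EOT.

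Protocol Table 6 schedules no AE visit after safety follow-up. But Protocol 8.1.2 says "Once an AE is detected, it should be followed until it has resolved or until it is judged to be permanent" and asks sites to record "The start and end dates, unless unresolved at final follow-up". Protocol 6.4.1 and Table 6 footnote d likewise extend AE follow-up past the safety visit where needed, for non-serious events too.

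**The concern.** In the non-serious, off-treatment branch, a participant whose event resolves on day 150 stays at risk to day 150 and counts as a resolution. A participant whose event is still open on day 150 leaves the risk set near EOT + 35 days. Whether someone is censored at the limit is therefore decided by what happens after it. Kaplan-Meier assumes that those censored have the same prospects as those who remain. Here the late resolvers are kept and the non-resolvers are dropped.

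The error runs one way. Compared with keeping open events at risk until last known unresolved, the resolutions are the same and the risk sets are equal or smaller, so the estimated resolution rate cannot be lower. What is at stake is the late part of the duration curves for known toxicities of this drug.

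**Working it through.** The documents give no figure for this point, so there is none to reproduce.

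**1. Mechanism, by hand (not an estimate of size).** Take ten non-serious events with onset at EOT. Six resolve, on days 5, 10, 15, 20, 60 and 90; four are still open at day 365. All rules give 40% resolved at day 30.
- SAP rule: the four open events leave at day 35, so two remain at risk. Day 60: 1 − 0.6 × 1/2 = 70%. Day 90: 100%.
- Open events kept at risk: day 60 is 1 − 0.6 × 5/6 = 50%; day 90 is 1 − 0.5 × 4/5 = 60%.
- Same limit for both outcomes: 40%, and no estimate after day 35.

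**2. Share of events affected (proxy only).** Protocol 1.3 reports AE frequencies in 72 subjects: "nausea (36%), diarrhea (35%), fatigue and rash (each 31%), and cough and vomiting (each 24". It also reports "Fourteen (19%) of the 72 subjects discontinued study treatment due to the following 10 AEs: diarrhea (n = 3", with one discontinuation for rash.
- Diarrhea: 0.35 × 72 = 25.2; 3/25.2 = 12%.
- Rash: 0.31 × 72 = 22.3; 1/22.3 = 4.5%, taken as 5%.

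**3. Size.** Assumed, not in the documents: a share p never resolves; the rest resolve exponentially with a 30-day median; affected and other events resolve alike; all late resolutions are recorded; cutoff is late. Let a be the share affected, L the limit in days from onset, and r(t) = (1 − p) × 2^(−t/30). Then:
- True proportion unresolved: S(t) = p + r(t).
- SAP rule, t > L: S(L) × [(1 − a)p + r(t)] / [(1 − a)p + r(L)].

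Example, p = 0.30, L = 42, a = 0.12, t = 180: 0.565 × (0.264 + 0.011)/(0.264 + 0.265) = 0.294, so 70.6% resolved against 68.9% true.

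| Day 180, % resolved | True | a = 5% | 12% | 25% | 50% |
|---|---|---|---|---|---|
| p = 0.30, L = 42 | 68.9 | 69.6 | 70.6 | 72.8 | 78.1 |
| p = 0.15, L = 42 | 83.7 | 84.2 | 84.9 | 86.3 | 89.5 |
| p = 0.15, L = 90 | 83.7 | 84.0 | 84.4 | 85.3 | 87.5 |

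At the proxy shares (5 to 12%) the excess is 0.3 to 1.7 points. For scale, with 25 events the 95% half-width is 1.96 × √(0.7 × 0.3/25) = 0.18. With p = 0.30, L = 42 and a = 0.12, the median is about 53.3 days against 54.2 true. With p = 0.15 the true median (38.4 days) falls before both limits and does not move. If no late resolution is recorded, day 180 returns to 68.9%.

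**4. Same limit for both outcomes.** Past L only unaffected events remain at risk, so the estimate is S(L) × (1 − a)S(t)/[(1 − a)S(L)] = S(t). The bias is gone when affected and other events resolve alike.

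**5. When they do not resolve alike.** Assume affected events have 50% never resolving and a 45-day median, and others 10% and 30 days; L = 42.

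| Day 180, % resolved | True | SAP rule | Same limit | Total gap | Removed by same limit |
|---|---|---|---|---|---|
| a = 12% | 83.6 | 88.1 | 87.6 | 4.5 | 0.5 |
| a = 25% | 78.2 | 87.7 | 86.5 | 9.5 | 1.2 |

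Most of this gap remains after both outcomes are treated the same way.

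**The case against.** The planned rule has a sensible basis: it stops open non-serious events at about the last scheduled AE assessment. Nothing shows how many later end dates sites will enter, and with none there is no such bias. This stands, and the point is conditional for that reason.

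The proxy is weak. Protocol 1.3 lists five serious diarrhea cases, so all three discontinuations for diarrhea could be serious and outside the rule. That study used continuous daily dosing, and Protocol 1.4 and 1.5 say the present regimens aim to reduce withdrawals for AEs. In the other direction, the proxy misses events open when treatment stops for another reason.

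The upper end of the range is demanding. A limit at day 42 puts EOT 7 days after onset. Protocol 5.5.1 allows a 14-day delay before a persistent AE forces withdrawal, which on that route puts the limit nearer 14 + 35 = day 49. With 5% never resolving and 12% affected, the formula gives 94.0% (L = 42) or 93.9% (L = 90) against 93.5%. Day 180 is also only an illustration, since the SAP names no timepoints.

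The consequence is low. The numbers resolved and censored are shown, all AEs are listed, and no efficacy result or futility decision uses this display. These arguments limit the size. They do not remove the asymmetry, because nothing in SAP 9.2.2 or 4.1.4 applies the limit to a recorded late resolution.

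**Conclusion.** The point holds as a minor one. For non-serious TEAEs off treatment, the written rule makes censoring depend on the later outcome. If late resolutions are recorded and some events stay open, Kaplan-Meier resolution rates past the limit are too high. The limit runs from EOT, so it falls at a different time from onset in each participant. Rates before it are unaffected, and the median moves only if it lies beyond it. Serious events and events on treatment are outside the rule. Grade 3 or higher displays are less exposed, because they end at improvement to Grade 2 or lower.

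The size cannot be known from the documents. It is about 0.3 to 1.7 points at day 180 under the assumptions above: 5 to 12% affected, 15 to 30% never resolving, limit at day 42 or 90, all late resolutions recorded.

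A reader might infer a defect of 4.5 to 9.5 points from the unequal-pattern case. The documents do not support that. The resolution patterns there are assumed, and only about 0.5 and 1.2 of those points come from treating the two outcomes differently. The rest is ordinary dependent censoring, which any limit near EOT + 35 days would share. Nor do the documents support affected shares of 25 or 50%, or reading the ten-event example as a likely result.

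**What to change.** **Main change, SAP 9.2.2.** Apply one limit to both outcomes: if a non-serious TEAE in a participant off treatment resolves or improves after the safety follow-up / EOT + 35 day limit (truncated as now), censor it at that limit. Report rates only at timepoints where enough participants remain at risk.

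**Sensitivity analysis.** Treat open non-serious off-treatment TEAEs as in the serious-TEAE rule, that is, at the earlier of data cutoff, study discontinuation and death. Alternatively, censor them at the last date confirmed ongoing, if the eCRF holds one later than the safety visit. Protocol 8.1.2 says "assessment should be made at each visit (or more frequently if necessary) of any changes in severity", but the documents do not say whether such a date is stored for each open event, and no AE visit is scheduled after safety follow-up. It may be the same date that the SAP already uses, which is why this is not the main change.

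**Cost.** One sentence and one derivation line, using dates the SAP rule already needs. Some late resolutions drop out of the main display (they stay in the AE listings), and late timepoints may not be estimable. The common limit still assumes that affected and other events resolve alike.
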